**Describing the characteristics of patients treated with bosutinib:**

The description of the population covered will present the characteristics of patients at time of initiation of treatment:

- demographic characteristics;
- medical history and comorbidities, duration between diagnosis and initiation of treatment and latest hematological, cytogenetic or molecular responses known (cytogenetic and molecular responses will be mentioned only if patient is in chronic phase);
- previous treatments: number of lines of treatment, medicinal products, better response during treatment, reasons for discontinuation of previous treatments.

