### **8.2. Secondary objectives**

Under real life conditions of use:

- To determine the safety profile of bosutinib: AEs that occurred during treatment with bosutinib, AEs which required changes to treatment with bosutinib, biological and hematological toxicities that occurred with bosutinib.
- To evaluate adherence of patients to treatment of bosutinib, with the aid of a self-questionnaire completed by patients (Morisky Questionnaire).
- To evaluate quality of life of patients treated with bosutinib, with a self-questionnaire completed by patients (FACT-leu version 4 - Questionnaire specific for leukemia)
- To describe the modalities of treatment with bosutinib under real life conditions of use (dose adjustment and reason for adjustment, dose intensity, relative dose

intensity; duration of treatment, temporary discontinuations/permanent discontinuations and reasons for such discontinuations).

- To evaluate the cumulative response rates: hematological (PHR/CHR), cytogenetic (CCyR / MCyR/ PCyR) and molecular response (MMR/CMR).
- To evaluate efficacy of treatment with bosutinib:
  - Progression-free survival at 1, 2 and 3 years of patients treated with bosutinib
  - Overall survival (OS) at 1, 2 and 3 years in patients treated with bosutinib
  - The percent transformation to AP/BC
- To describe the modalities of hematological, cytogenetic and molecular responses: median time to occurrence of response, median duration of response, type of response according to dose.
- To describe characteristics of patients treated with bosutinib (demographic characteristics; previous medical conditions, comorbidities; duration between time of diagnosis and initiation of treatment; previous treatments and better response under these treatments; duration of previous treatments, reasons for discontinuation of previous treatments; the last hematological, cytogenetic or molecular responses known).
- To evaluate cross intolerance between bosutinib and tyrosine kinase inhibitors prescribed previously.

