### 9.2.1. Criteria for inclusion

Patients must satisfy all of the following criteria for inclusion in order to be eligible.

- Male or female patient 18 years of age or older;
- Patient with BCR-ABL Philadelphia chromosome positive or negative CML, in chronic, accelerated or blast phase;
- Patient resistant or intolerant to previous therapy with TKI for CP, AP or CB CML other than bosutinib;
- Patient initiating treatment with bosutinib for treatment of CP, AP or BP phase Ph+ / - CML at the end of the inclusion visit or during the one month prior to it;
- Patient who has been informed that a method of contraception must be used if a risk of pregnancy exists.
- Patients who have been informed about the study and who signed the informed consent form.

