### 9.3. Variables

Patients will be identified indirectly via a unique number in the study (the centre no., patient no. pair).

The following “patient” data will be collected in the setting of the study at the usual consultation of patients in the centres.

Data	Role	Source
Compliance with criteria for inclusion and non-inclusion	Baseline characteristics	Inclusion visit
Demographic characteristics (year of birth, gender, weight, height, ECOG performance status)	Baseline characteristics	Inclusion visit
Diagnosis of CML (date of diagnosis, phase of CML at time of diagnosis, tests performed for diagnosis)	Baseline characteristics	Inclusion visit
Transcription of BCR-ABL gene at time of diagnosis	Baseline characteristics	Inclusion visit
Previous treatments of CML (type, dose, dosage, duration of previous treatment)	Baseline characteristics	Inclusion visit
Best response to previous treatments	Baseline characteristics	Inclusion visit
Reasons for change of previous treatments (if discontinuation for toxicity, description of the AE: type and grade)	Baseline characteristics	Inclusion visit
Phase of CML in the estimate of the participating doctor, at time of initiation of treatment with bosutinib	Baseline characteristics	Inclusion visit Follow-up visit
Evolution of mutational profile of BCR-ABL gene at time of initiation of treatment with bosutinib	Baseline characteristics	Inclusion visit Follow-up visit
Concomitant treatments at time of inclusion in the setting of management of CML	Baseline characteristics	Inclusion visit
Biological and hematological assessment data	Baseline characteristics Evaluation end point	Inclusion visit Follow-up visit
Hematological, cytogenetic and molecular response at time of inclusion and results	Baseline characteristics	Inclusion visit
Description of initiation of treatment with bosutinib (date of initiation, dose, dosage)	Baseline characteristics	Inclusion visit
Change to concomitant treatments in the setting of management of CML	Evaluation end point	Inclusion visit Follow-up visit
Description of treatment with bosutinib (changes to dose or dosage, temporary or permanent discontinuations of treatment)	Evaluation end point	Follow-up visit
Safety in treatment with bosutinib	Evaluation end point	Follow-up visit
Management of toxicities related to bosutinib (concomitant treatments, additional corrective medical measures)	Evaluation end point	Follow-up visit

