### **9.7.1. Statistical methods**

#### **Description of data**

Patients' characteristics will be evaluated overall and then separately for patients with CP, AP or BP Ph+/- CML, and by line of treatment. Other data will be separately evaluated for patients presenting with CP, AP or BP Ph+/- CML and then by treatment line.

A descriptive analysis of qualitative and ordinal variables will consist of the sample size and the frequency of each modality with its 95% confidence interval (CI). Quantitative variables will be described in terms of sample size, mean and median, standard deviation, SD, confidence interval.

The description of variables collected during follow-up of each patient will contain a presentation of parameters for each of the times of measurement.

Overall survival data and progression-free survival (PFS) will be described with Kaplan Meier curves. Median survival will be estimated and presented with its 95% CI.

The sample size of missing values for each variable analysed will be indicated in the tables of results. Key data will be made obligatory in the electronic CRF in order to control the percent of missing data, if applicable, with models based on maximization of the function of probability or of techniques of attribution will be used.

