**Response rate for patients in CP, AP or BP according to treatment line:**

- Cumulative hematological response:
  - o percent of patients presenting with a CHR during treatment with bosutinib (*best response according to the participating doctor's judgement*)
  - o percent of patients presenting with a PHR during treatment with bosutinib (*best response according to the participating doctor's judgement*)
- Cumulative cytogenetic response:
  - o percent of patients presenting with CCyR during treatment with bosutinib (*best response according to the participating doctor's judgement*)
  - o percent of patients presenting with MCyR during treatment with bosutinib (*best response according to the participating doctor's judgement*)
  - o percent of patients presenting with PCyR during treatment with bosutinib (*best response according to the participating doctor's judgement*)
  - o percent of patients presenting with mCyR during treatment with bosutinib (*best response according to the participating doctor's judgement*)
- Cumulative molecular response:
  - o percent of patients presenting with CMR (MR^4; MR4.5; MR^5) during treatment with bosutinib (*best response according to the participating doctor's judgement*)
  - o percent of patients presenting with an MMR (MR^3) during treatment with bosutinib (*best response according to the participating doctor's judgement*)

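### Baseline cytogenetic and molecular responses are to be shown for chronic-phase patients only, so the on-treatment cytogenetic and molecular rates in accelerated and blast phase cannot be read against the state at bosutinib initiation

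*Protocol*

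**What the plan says.** Section 9.7.3 of the protocol, under the description of patient characteristics, plans to present the latest known hematological, cytogenetic and molecular responses at the start of bosutinib. It then adds a parenthesis: "cytogenetic and molecular responses will be mentioned only if patient is in chronic phase". Hematological response carries no such limit.

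Other parts of the protocol do not share the restriction:

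- Section 8.2 includes "the last hematological, cytogenetic or molecular responses known" among the patient characteristics to be described, for all phases.
- Section 9.3 lists "Hematological, cytogenetic and molecular response at time of inclusion and results" as a baseline characteristic taken at the inclusion visit, with no phase condition.
- Section 9.7.1 sets the general rule that patients' "characteristics will be evaluated overall and then separately for patients with CP, AP or BP Ph+/- CML".

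On the outcome side, 9.7.3 has the heading "Response rate for patients in CP, AP or BP according to treatment line". Under it stand cumulative cytogenetic and molecular rates such as "percent of patients presenting with CCyR during treatment with bosutinib" and "percent of patients presenting with an MMR (MR 3 ) during treatment with bosutinib". They are best responses in the participating doctor's judgement.

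**The concern.** The protocol lists baseline cytogenetic and molecular response for collection and reports the on-treatment counterpart in every phase, yet tells the analyst not to show the baseline in two of the three phases.

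That matters because of how the outcome is counted. A patient is a responder if the response is present during bosutinib treatment; nothing requires it to be absent at the start. Entry is open to a "Patient resistant or intolerant to previous therapy with TKI for CP, AP or CB CML other than bosutinib". A patient who changed drug for intolerance may have been responding, and may begin bosutinib in complete cytogenetic response or major molecular response. That patient then enters the bosutinib rate whether or not bosutinib changed anything. Time to response, which runs from bosutinib initiation, is exposed in the same way, because a response already held can appear as a very early one.

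In CP the planned baseline description at least alerts a reader to this. In AP and BP it would not. These may also be small groups, in which one or two patients move a percentage visibly.

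**Working it through.** The protocol states no figure on this point. Its only design calculation, the precision for about 100 patients in 9.5, has no bearing on it. The check is first a comparison of sections, then a sensitivity calculation on stated assumptions.

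**Sections side by side**

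| Item | CP | AP and BP |
|---|---|---|
| Objective on last known responses (8.2) | included | included |
| Response at inclusion on the variable list (9.3) | listed | listed |
| General rule for characteristics (9.7.1) | described | described |
| Baseline hematological response (9.7.3) | shown | shown |
| Baseline cytogenetic and molecular response (9.7.3) | shown | **not shown** |
| On-treatment cytogenetic and molecular rates (9.7.3) | reported | reported |

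Only the fifth row differs by phase, and it conflicts with the first three.

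**Weight of one patient**

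In a stratum of n patients, each patient already in response at initiation and counted as a responder contributes 1/n to the rate.

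- The protocol gives no expected phase mix. As an assumption only, take the mix of the study 200 efficacy table in 7.3: (76 + 76)/(288 + 118 + 76 + 76) = 152/558 = 27.2%. With 100 patients that is about 27 in AP and BP together, or about 14 in each.
- n = 14: 1/14 = 7.1 points.
- n = 10: 1/10 = 10 points.
- n = 5: 1/5 = 20 points.

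**Effect of a carried-over share**

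Let R be the reported cumulative rate and b the share of the stratum already in that response at initiation and counted. The rate newly attained among the others is (R − b)/(1 − b). The documents do not give b, so a range is shown. For R the AP major cytogenetic response of 35% in the study 200 table is used as an illustration:

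| b | (0.35 − b)/(1 − b) | Newly attained |
|---|---|---|
| 0% | 0.35/1.00 | 35.0% |
| 5% | 0.30/0.95 | 31.6% |
| 10% | 0.25/0.90 | 27.8% |
| 20% | 0.15/0.80 | 18.8% |
| 30% | 0.05/0.70 | 7.1% |

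The BP row of that table is not used. It gives a complete cytogenetic response of 64% beside a major response of 30%, which cannot both hold if complete responses count within major ones.

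The same reported 35% is therefore compatible with quite different amounts of response gained on bosutinib, and the item that would help a reader judge this is the one that the parenthesis removes.

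**The case against.** The strongest reply is that the trouble lies in the outcome definition, not in the baseline table. Counting any best response during treatment mixes kept and gained responses in CP as well, and a baseline percentage printed beside an on-treatment percentage gives two marginal figures that do not show which patients kept and which gained. This stands, and it changes the remedy: deleting the parenthesis is necessary but not sufficient.

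A second reply is that the restriction may be deliberate. For suboptimal response, 9.7.3 refers CP patients to the ELN guidelines but defines the AP and BP case by hematological response alone. That could explain a hematological focus at baseline. It does not explain reporting cytogenetic and molecular response on treatment in those phases.

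Third, 9.7.3 describes best response to previous treatments and reasons for stopping them in all phases. This is useful context, but a past best response may have been lost before bosutinib began.

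Fourth, 9.7 lets the statistical analysis plan alter protocol plans, so this secondary table could be widened there. True, but a plan that follows the protocol would inherit an express restriction that contradicts the protocol's own objective.

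A reader might go further and infer one of the following, none of which the documents support:

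- That all AP and BP response rates lack a baseline. Hematological response at initiation is described in every phase.
- That the baseline data will be missing. Section 9.3 lists them without a phase limit.
- That a baseline result exists for every patient. Section 9.1 requests no additional examination, so a result exists only where routine care produced one.
- That the AP and BP rates are inflated by a known amount. Neither the phase mix nor the share already in response is given, and that share could be zero.

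**Conclusion.** The point holds as an internal contradiction with a limited but real consequence. One parenthesis in 9.7.3 conflicts with 8.2, 9.3 and 9.7.1 and leaves the AP and BP cytogenetic and molecular response rates without the state at initiation against which to read them.

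The size cannot be estimated from the protocol. What can be said is that each carried-over responder contributes 1/n, about 7 points if a phase has 14 patients. That number rests on borrowing the study 200 phase mix, on 100 inclusions and on an equal split between AP and BP. The calculation with b shows sensitivity and is not a forecast.

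The matter affects secondary descriptive results only. Neither primary objective, on related adverse events or on permanent discontinuation after them, depends on it. It should be corrected because the correction is cheap, but it does not threaten the study's main results.

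**What to change.** 1. Delete the parenthesis in the patient-characteristics part of 9.7.3, so that it agrees with 8.2, 9.3 and 9.7.1.
2. Describe the last known cytogenetic and molecular response at bosutinib initiation for CP, AP and BP alike, with not tested as its own category. Since 9.2.1 allows bosutinib to have started up to a month before the inclusion visit, state that the result must date from on or before the start of bosutinib.
3. For each phase, cross-tabulate response at initiation against best on-treatment response, patient by patient. Alternatively, report beside each cumulative rate the rate among patients not already in that response at initiation, with its denominator. Doing this for CP too settles the same ambiguity there.

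The cost is some extra table rows. The baseline responses are already on the variable list, so no new visit or test is needed. Where routine care produced no result, the patient falls in the not-tested category, and the size of that category is itself informative.

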**Evaluating cross-intolerance between bosutinib and previous targeted therapies:**

Cross-intolerance will be defined by percent of patients who permanently discontinued bosutinib because of an adverse event which had resulted in discontinuation of a previous treatment (imatinib, dasatinib, nilotinib). Cross intolerance will be estimated for all AEs, but also by type of adverse event.

Analysis of secondary objectives will be detailed in the statistical analysis plan.

**9.7.4. Representativeness of participating centres**

A description of a sample of centres will be made *post hoc* based on data on identification of participating doctors in each centre (gender, age, geographical location). It then will be verified that the sample of participating doctors is representative of hematologists in France in terms of sample size and type of centre in order to ensure outside validity of the study.

**9.8. Quality control**

**9.8.1. Set up of participating doctors**

It will be offered to doctors preselected to participate in this study. This participation will be made tangible by signature of the financial agreement. Validation of the latter, a visit for set up of study on site will be organized by the Clinical Research Associate in order to present the study and all related documents to the participating doctor, as well as to members of his staff that he has designated, if applicable.

### **9.8.2. Logistics and monitoring of participating centres**

Throughout the study, participating doctors will be contacted to ensure the understanding and compliance with the protocol and the electronic questionnaire. All contacts will be documented.

Study Monitors will be in charge of performing at least one monitoring visit per year and per centre, as well as one closing visit. At these visits, the monitors will be in charge of ensuring the understanding and compliance of the protocol by the doctor, the existence of patients included, that the data recorded in the case report form are in fact identical to source data (verification of a minimum number of clinically relevant and major data defined beforehand in agreement with the scientific committee), of verifying the good keeping up-to-date of the Site Master File (SMF), and of verifying the reporting of AE to the Pfizer pharmacovigilance department (*see 11 Erreur ! Source du renvoi introuvable.*)

Key indicators of proper conduct of this study (number of active centres, number of patients included, number of follow-ups performed, etc.) will be generated using the study database. This database will make it possible to edit study progress reports which will enable to generate the sending of reminders to centres.

### **9.8.3. Quality and accuracy of data**

The participating doctor will be responsible for collection of reports of all clinical data, of safety data and laboratory data entered in the eCRF and/or other forms of data collection (source documents), and must ensure that they are accurate, authentic, attributable to the patient, complete, consistent, readable, contemporaneous and available if needed.

In order to enable controls and/or audits by the regulatory authorities or by Pfizer, the participating doctor accepts to keep registries including the identity of all participating patients (sufficient information to review the dossiers (e.g. eCRF and hospital medical dossiers)). The participating doctor will keep all original signed informed consent forms, copies of serious adverse event reports, source documents and medical results leading to decisions on treatment.

## **9.9. Limitations of study methods**

This protocol has been built in a manner so as to best respond to the objective set for this observational study. However, the latter has certain limitations which must be discussed and which should be taken into account at time of the initiation of the study and utilization of results.

### **9.9.1. Selection bias of participating doctors**

Participating doctors will be recruited from a baseline survey representative of different centres specializing in management of CML in France. However, the voluntary characteristic of participation of doctors in the study is a usual selection bias for this type of study. This is why the two populations of doctors (those accepting and those refusing to participate) will be compared. In the event that major deviations in comparison with the survey database are observed, this will be taken into account by making corrections and or by discussing results of the study with regard to the differences observed.

### **9.9.2. Selection bias of patients**

The representativeness of the sample of the study compared to the target population is basic in order to be able to extrapolate results of the study to the target population. The representativeness of the sample depends on internal validity (precision of estimates and selection criteria of study population – the patients) and the outside validity (plan and fluctuations of sampling).

The representativeness of patients included is a potential selection bias in observational studies. Conscious selection or not of patients in the study by participating doctors is inevitable. Participating doctors will be asked to include sequentially and exhaustively all patients who satisfy eligibility criteria for the study up until the end of the inclusion period in order to limit this bias. Parameters on representativeness of patients included will be controlled by the set-up of a registry of non-inclusion up until the end of the inclusion period.

### **9.9.3. Patients lost to follow-up during follow-up**

Special attention will be paid to patients who discontinue the study or that the participating doctor has not seen in a visit as the results of the observational characteristic of the study (frequency of visits for follow-up of patients can vary depending on doctors and patients). For patients lost to follow-up, a questionnaire on last news from the patient (end of study) will be completed by the participating doctor. Statistical analyses will compare characteristics of patients included and who participated in the entire duration of the study in patients included and lost to follow-up and/or who discontinued the study before the end of follow-up.

### **9.9.4. Measurement bias**

Special attention will be paid to patients who discontinue the study or that the participating doctor does not see at a visit as a result of the observational characteristic of the study (the frequency of visits for follow-up of patients can vary depending on doctors and patients). For patients lost to follow-up, a questionnaire on the patient's last news/end of study will be

completed by the participating doctor. Statistical analyses will compare the characteristics of patients included and who participated in the entire duration of the study in patients included and lost to follow-up and/or who discontinue the study before the end of follow-up.

